Subjects will be randomized into one of the two groups. Twelve subjects will be allocated to the test group and another 12 subjects to the control group. The subject will not know which group he or she belongs as blinded allocation. Randomization will be determined by the last digit of the chart number (odd number goes to Group A and even number goes to Group B) but if one group has two subjects more than the other group, the next subject will automatically be enrolled in the lesser number group to ensure timely even distribution. The assignment of control or experimental group to Group A or B will be written by the primary surgeon (Principle Investigator) in a concealed envelop before recruiting patients. This ensure the clinical examiner be blinded throughout the study. This randomization will prevent any operator bias.

E. Pre-surgical Preparation V1

Prior to the surgical visit, the subject will be asked if they are still willing to participate in the study and their medical history will be reviewed. Clinical measurements of PD, BOP, CAL, PI and GI will be recorded and peri-implant bacterial and crevicular fluid samples will be collected. A prophylaxis or a periodontal maintenance will be completed based on the subject's prior diagnosis. In addition, a set of intraoral photographs will be taken, one standardized peri-apical radiograph, and maxillary and mandibular impressions will be taken. Articulating paper will be used to check the occlusal contact of the implant crown, if there is obvious heavy contact or lateral interference, occlusal adjustment will be made.

F. Surgical procedure V2

The subject will be asked if they are still willing to participate in the study and their medical history will be reviewed. The subject's vitals of blood pressure and heart rate will be taken. During this visit, intraoral photos will be taken and all surgeries will be performed under local anesthesia using one or more of the following medications:

- Lidocaine with epinephrine, (Xylocaine 2%®-Epinephrine 1:100,000 and 1:50,000, Dentsply Pharmaceutical, York, PA, USA).
- Articaine (Septanest 4%®-Epinephrine 1:100,000, Dentsply Pharmaceutical, York, PA, USA).
- Mepivacaine (Polocaine 2%®-Levonordefrin 1:20,000, Dentsply Pharmaceutical, York, PA, USA).

After local anesthesia, the width of the keratinized tissue around the implant will be measured by periodontal probe and the thickness of the peri-implant mucosa will be measured with endo file and stopper.

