absorbable cross-link collagen membrane will be trimmed to an appropriate size and shape to completely cover the implant site, and extend about 3-5mm beyond on the facial aspect. The membrane will be tucked under the sub-periosteal flap. Care will be taken to ensure that the membrane is resting on bone. Bone grafting and membrane placement for peri-implant infrabony defect is a standard of care procedure.

3) Site closure

Soft tissue will then be sutured with PTFE sutures (Cytoplast - PTFE suture) using either a simple interrupted technique or a criss-cross technique. Primary closure of the site will be attempted. The main objective of the sutures will be the stabilization of the wound. Sutures will be removed 10-14 days after.

5) Post-Operative Care

All subjects will be prescribed 500mg of amoxicillin to take 3 times a day for ten days.

If the subject is allergic to Amoxicillin, they will be prescribed 250 mg of Zithromax 6 tablets total /sig. 2 tablets the 1st day and Q.D. (1 x per day) until gone. In addition, the subject will be prescribed 600 mg of ibuprofen, taken as needed, for pain control.

Subjects will be instructed to rinse twice daily with chlorhexidine for 1 minute, 2 times per day for the first week. Following the first week, the subject will apply chlorhexidine with a Q-tip for another 3 weeks. They will also avoid brushing or touching the area of implant placement for 2 weeks. Subjects will be informed that the sutures will be removed 2 weeks following the surgical appointment.

G. Outcomes

The primary outcome examined in this study will be the clinical results. Secondary measurements will include radiographic assessments and post-op pain assessment. Exploratory measures will include biomarker profile and microbiological examination.

2 (± 1) Week Follow-Up (V3)

The subject will return in 2 weeks (± 1 week) for follow up care. The subject will be asked if they still are willing to participate in the study and their medical history will be reviewed. The removal of the sutures or partial removal will be determined depending on the healing.. The intensity and duration of post-operative pain assessment will be based on patient-reported days and scores using a 11-point numeric pain rating scale (NRS-11) (Jensen et al. 1989; Matys and Dominiak 2016). In addition, a standardized radiograph and intraoral photographs will be taken, BAC and PICF will be collected, and clinical measurements of GI and PI will be taken.

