4 (± 1) Week Follow-Up (V4)

The subject will return in 4 weeks (± 1 week) for follow up care. The subject will be asked if they still are willing to participate in the study and their medical history will be reviewed. If sutures are present, they will be removed. Intraoral photographs will be taken. BAC and PICF will be collected and clinical measurements of GI and PI will be taken. The subject will be mailed a compensation of a \$40 check from HSIP at the conclusion of this visit.

12 (± 1) Week Follow-Up (V5)

The subject will return in 12 weeks (± 2 week) for follow up care. The subject will be asked if they still are willing to participate in the study and their medical history will be reviewed. Intraoral photographs will be taken. A prophylaxis or a perio maintenance will be completed. In addition, BAC and PICF will be collected and clinical measurements including PD, BOP, CAL, PI, and GI will be taken. The subject will be mailed a compensation of a \$40 check from HSIP at the conclusion of this visit.

Re-evaluation (± 2) 24 Week Follow-Up (V6)

The subject will return in 24 weeks (± 2 week) for follow up care. The subject will be asked if they still are willing to participate in the study and their medical history will be

reviewed. A standardized radiograph and intraoral photographs will be taken. A prophylaxis or a periodontal maintenance will be completed. In addition, BAC and PICF will be collected and clinical measurements including PD, BOP, CAL, PI, and GI will be taken. Peri-implant mucosal thickness and the width of the keratinized tissue will be measured. A final impression will also be taken. The subject will be mailed a compensation of a \$40 check from HSIP at the conclusion of this visit.

Radiographic assessment of the alterations in alveolar bone fill and crestal level will be done through the use of standardize peri-apical x-rays. One peri-apical x-ray may be taken at the screening visit (V0), if there is no current x-ray to reference or if inclusion and exclusion criteria cannot be determined. Standardized peri-apical x-rays will be obtained at three different time points (before surgery (V1), two weeks post-surgery (V3), and at the re-evaluation 24 week visit (V6). The ridge dimensions obtained from these x-rays will then be compared to the baseline measurements to identify changes.

II) Microbial profile (BAC) and Peri-implant crevicular fluid (PICF) analysis

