PICF samples will be obtained at Pre-surgical Preparation (V1), 2 week (V3), 4 week (V4), 12 week (V5) and re-evaluation-24 week (V6). These samples will be used for bacterial DNA and biomarker analysis. Samples will be collected with sterile paper point and strips. The sites sampled will be isolated with cotton rolls to keep the area dry and free of salivary contamination. A gentle air blow will be applied perpendicularly before sampling. For biomarker analysis, a perio strip will be inserted into the crevice until mild resistance is felt and left for 30 seconds. For microbial profile, a paper point will be inserted for 10 seconds. Two sampling per assays will be collected with 90-second intervals. The paper point and paper strip will be carefully removed to avoid contamination from contact with other tissues and to avoid trauma to the site. The samples will then be transferred to sterile micro centrifuge tubes containing protease inhibitors and stored at – 80 °C until further processing of the biomarkers analysis. All

the sampling procedures are established and published by our group (Kinney et al. 2014; Wang et al. 2016).

Examiners calibration

Calibration of the examiner will be performed through a training exercise with a calibrated examiner prior to the beginning of the study. The calibrated examiner will observe and confirm the accuracy of the clinical measurements of PI, GI, and PD of the study examiner (>0.8 agreement between examiners will be considered calibrated).

IV. Statistical Analysis: Sample Size

This study will have a sample size of 24 subjects, 12 in each of the groups.

The study power was calculated using the software nQuery Advisor v7.0 (Statistical Solutions, Saugus MA, USA). A difference of 2.0mm between groups was considered as clinically significant. The power value was evaluated for probing depths at 6 months after the surgery. A “p” value of less than 0.05 will be considered statistically significant.

Data Analysis

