Mean values, standard deviations, and medians will be calculated for clinical and radiographic measurements. We will examine the univariate association of the probing depths with the detoxification method used. We will also attempt to examine the association of bacterial load with various combinations of clinical and radiographic parameters using multiple logistic regression, but acknowledge that we will be restricted by our sample size to at most two or three predictors in any model. Changes of the parameters over time within each group as well as differences between groups will be analyzed using the repeated measure of analysis of variance.

V. Regulatory Considerations

Surgeries and related procedures would be performed at no cost for the patients included in the study. Three free dental cleaning and \$120 compensation will be given to the patients.

Study reporting

1. Adverse events

Any adverse event, including both observed or volunteered problems, complaints, or symptoms, are to be recorded on the Adverse Event Case Report Form. The intensity of the adverse event will be characterized as mild, moderate or severe as follows:

- MILD events are usual transient, requiring no special treatment, and do not interfere with the subjects daily activities.
- MODERATE events traditionally introduce a low level of inconvenience of concern to the subject and may interfere with daily activities, but are usually ameliorated by simple therapeutic measures.
- SEVERE events interrupt a subject's usual daily activity and traditionally require systemic drug therapy or other treatment.

When intensity changes occur more frequently than once a day, the maximum intensity for the event should be listed. If the intensity category changes over a number of days, then these mini-events or changes should be recorded separately (i.e. having distinct onset days).

The investigator will determine the relationship of the adverse event to the study test material.

One of the following determinations will then be used to document the relationship of the adverse event to the study test material:

- NOT RELATED
- POSSIBLE
- PROBABLE

ANY SERIOUS AND UNEXPECTED ADVERSE EVENT INCLUDING HOSPITALIZATION OR DEATH DUE TO ANY CAUSE, WHICH OCCURS DURING THIS INVESTIGATION, WHETHER OR NOT RELATED TO THE STUDY, MUST BE REPORTED IMMEDIATELY (WITHIN 24 HOURS) TO THE PRINCIPAL INVESTIGATOR.

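### Cleaning is listed after sampling and scoring at V1 but before them at V5 and V6, and no order is fixed, so within-group changes may carry a same-day cleaning effect

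*Combined protocol and SAP*

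**What the plan says.** **V1 (section III.E).** PD, BOP, CAL, PI and GI are listed first. The text continues: "peri-implant bacterial and crevicular fluid samples will be collected. A prophylaxis or a periodontal maintenance will be completed based on" the subject's prior diagnosis. Cleaning is listed last.

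**V5 (section III.G, 12-week visit).** "A prophylaxis or a perio maintenance will be completed. In addition, BAC and PICF will be collected and clinical measurements including PD, BOP", followed by CAL, PI and GI. Cleaning is listed first.

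**V6 (section III.G, 24-week visit).** "A prophylaxis or a periodontal maintenance will be completed. In addition, BAC and PICF will be collected and clinical measurements including PD, BOP", followed by the same measures. Cleaning is again listed first.

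**Antimicrobials (section III.F, Post-Operative Care).** Both arms rinse with chlorhexidine for one week. Then: "Following the first week, the subject will apply chlorhexidine with a Q-tip for another 3 weeks". For antibiotics: "All subjects will be prescribed 500mg of amoxicillin to take 3 times a day for ten days". The alternative is: "If the subject is allergic to Amoxicillin, they will be prescribed 250 mg of Zithromax 6 tablets total".

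**Sampling.** Bacterial and crevicular-fluid samples are taken at V1, V3, V4, V5 and V6. The sampling section covers isolation, drying, insertion time and intervals, but not whether sampling comes before cleaning.

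**Analysis (section IV, Data Analysis).** "Changes of the parameters over time within each group as well as differences between groups will be analyzed" by repeated-measures analysis of variance.

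**Role of the measures.** Section II places PI and BOP in the primary outcome set, and BOP is in the Aim 1 hypotheses. Bacterial and fluid data are exploratory. Appendix A scores PI over the teeth, six surfaces each, and BOP at six sites per implant.

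**The concern.** A change from baseline can be read as a treatment effect only if the two readings are taken under the same conditions. A plaque score read straight after a cleaning describes the cleaning, not the plaque the patient brought to the visit. The same applies to a bacterial sample if the cleaning includes the study implant, which the text does not exclude. If V1 is read before cleaning and V5 and V6 after it, part of any fall in plaque or bacterial load within an arm could come from the cleaning alone.

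The other two follow-up samples cannot stand in, because V3 and V4 are taken during or close to the chlorhexidine course. As listed, then, no follow-up sample is taken wholly under V1 conditions, yet within-group change over time is a planned analysis. A plaque score or sample taken after cleaning cannot be corrected later in the analysis.

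**Working it through.** The plan states no figure on this point, so there is nothing to reproduce. The check compares the listed orders, lays the visit windows over the drug courses, and then examines the separate matter of using V1 in the arm comparison.

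**1. Listed order**

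| Visit | Listed first | Listed after |
|---|---|---|
| V1 | PD, BOP, CAL, PI, GI; then samples | cleaning |
| V5 | cleaning | samples; then PD, BOP, CAL, PI, GI |
| V6 | cleaning | samples; then PD, BOP, CAL, PI, GI |

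Table I marks which procedures occur at each visit and gives no sequence.

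**2. Windows against drug courses**

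Day 0 is surgery and first doses are assumed on day 1. Chlorhexidine runs 7 + 21 = 28 days (days 1-28). Amoxicillin runs days 1-10. Azithromycin is 2+1+1+1+1 = 6 tablets, so days 1-5. Windows come from Table I, with V5 at plus or minus 2 weeks.

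| Visit | Permitted days | Days on chlorhexidine | Other |
|---|---|---|---|
| V3 | 7-21 | 15 of 15 | days 7-10 also on amoxicillin (4 days); 0 on azithromycin |
| V4 | 21-35 | 8 of 15 (days 21-28) | remaining days at most 35 - 28 = 7 after it |
| V5 | 70-98 | 0 | at least 70 - 28 = 42 days after it |
| V6 | 154-182 | 0 | at least 154 - 28 = 126 days after it |

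If dosing starts on day 0, the V4 count is 7 instead of 8. V6 is 154 - 98 = 56 to 182 - 70 = 112 days after the V5 cleaning. So V5 and V6 are clear of chlorhexidine. Read before that day's cleaning, they would match V1 on both points. BOP is not recorded at V3 or V4, so the chlorhexidine caveat does not reach it.

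**3. Separate point: V1 as covariate or as outcome level**

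Assumptions, none of them from the documents: bacterial load analysed on a continuous scale, a constant arm difference of 1.2 SD at V3 to V6, equal correlation r between visits, two-sided 0.05. The 10 completers per arm are taken from the plan's sample-size basis. At r = 0.5:

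- *Mean of V3-V6 adjusted for V1.* SD = sqrt((1+3r)/4 - r²) = sqrt(0.625 - 0.25) = 0.612. Noncentrality = 1.2/(0.612 × sqrt(2/10)) = 4.38 on 17 df. Power 98%.
- *ANOVA group term with V1 as one of five levels.* Effect = 1.2 × 4/5 = 0.96. SD = sqrt((1+4r)/5) = 0.775. Noncentrality = 0.96/(0.775 × sqrt(2/10)) = 2.77 on 18 df. Power 75%.
- *ANOVA group-by-time term.* Sum of squares of the profile (0, 1.2, 1.2, 1.2, 1.2) about its mean = 0.96² + 4 × 0.24² = 1.152. Noncentrality = (10/2) × 1.152/(1 - r) = 11.52 on F(4,72). Power 75%.

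The same formulas give 98%, 86% and 59% at r = 0.3, and over 99%, 64% and 94% at r = 0.7. The gain does not depend on cleaning order.

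If the arm difference is wholly masked at V3 and V4, the mean effect halves to 0.6 SD. At r = 0.5 the V1-adjusted V3-V6 mean then has 54% power, the group-by-time term 92%, and the V1-adjusted V5/V6 mean 95%.

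**The case against.** **The lists may be inventories.** The linking words at V5 and V6 add an item and do not sequence it. Table I puts the cleaning row above sampling and clinical measures for every visit, V1 included. Read as a sequence, it would remove the asymmetry. V1 also lists probing before fluid sampling, whereas V5 and V6 list the reverse. This stands. The documents support an unspecified order with a reversed listing; they do not show that staff will clean first.

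**The aims are comparative.** Aims 1 to 3 compare laser with mechanical debridement, and power was considered for PD at 6 months. This also stands. A reader might infer that the laser-versus-control result is biased. It is not: cleaning, chlorhexidine, antibiotic and visit text are the same in both arms. Shared antimicrobials or cleaning could shrink an arm difference in bacterial load, by an amount the documents do not give.

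**A false-positive rate is tempting.** One could assume a cleaning shift and compute how often a within-arm change would be falsely significant. The documents give no shift, and no direction for BOP. The null of no change is also unlikely after flap surgery, debridement and grafting. No such rate is claimed.

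**V3 and V4 are legitimate data.** They describe healing under the prescribed regimen, which suits the stated interest in dynamic change. Agreed: they need a caveat and should be kept.

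What remains is that the within-group analysis is planned, the visit text as written invites unlike readings, and nothing in the plan prevents it.

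**Conclusion.** The point holds in conditional form. If the listed order is followed, V5 and V6 values of PI, BOP and bacterial samples are read after a cleaning and compared with a V1 value read before one, so the planned within-group changes include a same-day cleaning effect of unknown size. For PI this holds whether or not the implant itself is cleaned, since the score covers the teeth. For the samples and BOP it also assumes that the cleaning includes the study implant.

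For V3 and V4 the overlap with chlorhexidine is a matter of interpretation for within-group change. The arm comparison is not biased, the bacterial data are exploratory, and no claim is made about PD at 6 months. The point merits action because it is cheap to prevent beforehand and cannot be repaired afterwards.

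Adjusting the bacterial arm comparison for V1 is a separate improvement: 98% power against 75% for either ANOVA term under the assumptions shown. It does not follow that the V3-V6 average should be the single Aim 2 test. That is a trade-off, and the average does badly if early differences are masked.

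**What to change.** 1. In section III.G, at both V5 and V6, state: 'BAC and PICF samples are collected and PI, GI, PD, BOP and CAL are recorded before the prophylaxis or maintenance, as at V1.'
2. In section IV, Data Analysis, note that V3 and V4 samples were taken during or near antibiotic and chlorhexidine use, and that within-group changes to those visits are to be read in that light.
3. Separately, in section IV, adjust the between-group comparison of bacterial load for the V1 value and do not enter V1 as an outcome level. Which follow-up visits form the Aim 2 contrast is left to the investigators.

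The cost is text only. The cleaning moves to the end of two visits. No visit, sample or treatment is added or dropped, and the V1 value is already collected. Item 1 needs to be in place before V5 and V6 visits take place.

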| 
 • Subjects, aged 18 - 85 years • Physical status according to the American Society of Anesthesiologists (ASA) I or II, which includes patients who are systemically healthy or suffer under mild to moderate, but well controlled systemic diseases. • Subjects having a minimum of 1 dental implant with peri-implantitis. • Dental implants with peri-implantitis ≥ 2 threads (or $\geq 2\text{mm}$) exposed (infrabony defect) identified on the radiograph and pocket probing depth (PPD) $\geq 5\text{mm}$, with bleeding on probing (BOP) and/or suppuration (pus) • The implants are in function for at least 6 months • Only rough surface implant will be included in this study |
| Exclusion Criteria |

- Long-term use of antibiotics > 2 weeks in the past two months
- Obvious malpositioning of the dental implants
- Subjects taking medications known to modify bone metabolism (such as bisphosphonates, corticosteroids, Hormone replacement therapy for menopausal women, parathyroid hormone, Denosumab, strontium ranelate)
- Pregnant females or those planning to become pregnant
- Subjects with a history of major diseases, oral cancer, sepsis or those having adverse outcomes to oral procedures in the past, will be excluded
- Mobility of dental implants
- History of alcoholism or drug abuse
- Current smokers
- Diseases of the immune system or any medical condition that may influence the outcome (uncontrolled diabetes (HbA1c >8))
- Uncontrolled systemic disease or condition known to alter bone metabolism, like Osteoporosis, Osteopenia, Hyperparathyroidism, Paget's disease

Premature Exclusion Criteria

- The researcher believes that it is not the best interest of the subject to stay in the study
- If the subject becomes ineligible to participate based on the exclusion criteria
- If the subject's medical condition requires interventions which preclude involvement in the study (radiation therapy, chemotherapy, etc)
- If the subject does not follow study related instructions
- The study is suspended or canceled.

D. Randomization

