Reports of serious or unexpected adverse events will be made immediately by telephone or fax to: **[name] [contact]**

This telephone report or fax must be followed within 5 days by a written summary fully documenting the event in order to permit the Principal Investigator to file a report which satisfied regulatory guidelines.

All serious and unexpected adverse events associated with the use of the study test material will be immediately reported to appropriate regulatory agencies by the Principal Investigator.

Adverse events reporting will proceed according to the University of Michigan guidelines for standard AE reporting.

2. Discontinuation and replacement of subjects

- Any subject found to have entered the study in violation of this protocol will be withdrawn from the study after discussion with the Principal Investigator

- An effort will be made to determine why any subject discontinues the study prematurely. This information should be recorded on the appropriate case report form.
- As stated in the informed consent, all subjects reserve the right to withdraw from the study at any time.
- Any female subject that becomes pregnant during the study will be withdrawn from the study.
- Any subject whose condition changes after entering the study, so that he or she no longer meets the inclusion or exclusion criteria, will be withdrawn from the study.
- Any subject who requires the use of an unacceptable concomitant medication will be withdrawn from the study.
- The investigator will discontinue any subject from the study if, in the investigator's opinion, it is not in the subject's best interest to continue.
- The date the subject is withdrawn from the study and the reason for discontinuation will be recorded on the case report form.
- When a participant is lost to follow-up, that is, fails to return for study visits, a reasonable effort should be made to contact the participant in order to determine why the subject failed to return. This information will be documented on the case reporting form (CRF). When a participant is withdrawn from the study, regardless of the cause, all evaluations required at the scheduled end of study day should be performed.
- Subjects discontinued for adverse events will not be replaced.

3. Data reporting and case report forms (CRFs)

Data reflecting participant experience with the protocol under investigation will be reported to the Principal Investigator and the data recorded on CRFs

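### Minor: read literally, the exit rule asks for the end-of-study radiograph in a subject withdrawn for pregnancy, and no visible text exempts her

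*Combined protocol and SAP*

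**What the plan says.** Four provisions bear on this point.

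- **Exit rule** (Study reporting, item 2, Discontinuation and replacement of subjects): for a withdrawn participant, "regardless of the cause, all evaluations required at the scheduled end of study day should be performed".
- **Pregnancy** (same list): "Any female subject that becomes pregnant during the study will be withdrawn from the study". At entry, the Exclusion Criteria in III.C rule out "Pregnant females or those planning to become pregnant".
- **End-of-study visit** (III.G, 24-week re-evaluation, V6): "A standardized radiograph and intraoral photographs will be taken. A prophylaxis or a periodontal maintenance will be completed". The X-ray row of Table I also shows a standardized film at V6, after those at V1 and V3.
- **Use of the films** (III.G, paragraph on radiographic assessment): "The ridge dimensions obtained from these x-rays will then be compared to the baseline measurements to identify changes".

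Two further provisions affect how firmly the exit rule binds. The discontinuation section notes that "all subjects reserve the right to withdraw from the study at any time". Under Deviation from the Protocol, the investigator needs written IRB approval before departing from the protocol, and the only exception described is a medical emergency.

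**The concern.** The exit rule is more than silent about pregnancy. It is expressly universal as to cause, and one of the causes it covers is a condition in which staff would ordinarily hold back a radiograph that is not needed for care. Someone who follows the sentence faithfully would arrange an X-ray, for a measurement the trial wants, in a pregnant woman who is no longer a participant. Someone who sensibly leaves it out is departing from the written rule, in a protocol that restricts departures. A safety-relevant instruction should not depend on staff setting its wording aside.

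At stake is the handling of an individual subject. The trial's statistical conclusions are not affected.

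**Working it through.** No arithmetic applies, because the point depends on no sample size, rate or error probability. The check is whether the provisions, placed side by side, produce the instruction and whether anything visible removes it.

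1. **Does the rule reach pregnancy?** Yes. Pregnancy during the study requires withdrawal, and the exit rule covers withdrawal for any cause. Both stand in the same list.
2. **Which evaluations are meant?** Those of the scheduled end-of-study day. The protocol does not attach that label to V6. V6 is the last scheduled visit in both III.G and Table I, so identifying the two is an inference, but a safe one.
3. **Does that set include a radiograph?** Yes, in the V6 text and again in Table I. The V6 set also covers medical history, photographs, prophylaxis or maintenance, impression, bacterial and crevicular fluid samples, the clinical measures and mucosal thickness. The radiograph is the only item in the set that involves X-ray exposure.
4. **What is the film for?** The stated use is comparison with baseline to identify change, which is a study measurement. No clinical use of the V6 film is stated, and none is ruled out.
5. **Is there an exemption?** In the visible text, pregnancy appears only as an exclusion criterion and as a reason for withdrawal. Neither place mentions radiographs, and the radiographic paragraph does not mention pregnancy.
6. **May staff simply omit it?** The case report form conventions provide codes for not applicable and not done. Those codes record an omission; they do not authorize one. The deviation rule still applies.

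**Size.** The exposure in question is one film, the last of three scheduled standardized films, per affected subject. The number of affected subjects cannot be derived: the age range is 18 to 85, no sex mix is given, and women planning pregnancy are excluded. The power statement concerns a different variable: "The power value was evaluated for probing depths at 6 months after the surgery". A missing V6 film therefore does not enter the sample-size basis.

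**The case against.** The strongest reply is that the sentence was never meant to override clinical judgement. Its verb is *should*, while the neighbouring items mostly use *will*. Subjects can withdraw at any time. At each visit after screening they are asked whether they are still willing to take part, and their medical history is reviewed. The consent pages are not available, and the discontinuation section itself refers to the consent form, so a condition on pregnancy and X-rays may stand there. All of this lowers the chance that a film would actually be taken. None of it is a written exemption, and if the consent form does contain one, the protocol sentence ought to agree with it.

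A reader might be tempted by several stronger conclusions that the documents do not support.

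- **That the film is research-only.** The protocol states a study use but never says it is the sole use, and V6 is also described as follow-up care after graft surgery.
- **That the documents show harm from such a film.** They do not, and they do not give radiography as the reason for excluding pregnancy. The case for an exemption is precautionary: exposure for a measurement, with no stated benefit to a subject who has left.
- **That unscheduled exit values would corrupt the 24-week analysis.** The rule does not say when exit evaluations are done. However, nothing says exit values will be analysed as V6 values, and the date of withdrawal is recorded. This is missing detail, not a shown error.
- **That early exit probing should be barred**, because V3 and V4 are limited to gingival and plaque indices. No harm from early probing is documented, and crevicular sampling at weeks 2 and 4 already enters the site: "a perio strip will be inserted into the crevice until mild resistance is felt". A bar would also discard the only post-surgery probing depth from subjects who leave early.

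**Conclusion.** The point holds as a minor wording defect with a safety aspect. A rule that is explicitly universal, combined with mandatory withdrawal for pregnancy and a radiograph at the end-of-study visit, literally asks for a study film in a pregnant subject, and no visible text says otherwise.

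The conclusion rests on two assumptions: that the end-of-study day is V6, and that the unavailable consent pages do not already settle the matter. If they do, what remains is a mismatch between two study documents. Occurrence should be rare, and the consequence is at most one film per affected subject. No effect on power, type I error, randomization or the primary conclusion is claimed.

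**What to change.** Add to the exit sentence: *except that no study radiograph is taken in a subject who is pregnant (a clinically needed film remains at the clinician's discretion).*

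Optionally, add a second sentence: *Exit evaluations are done at withdrawal, with the subject's agreement, and are analysed at their actual week after surgery.* This supplies the missing timing and keeps every exit measurement a subject is willing to give, including early probing depths.

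The cost is a short amendment with IRB approval and, for a subject withdrawn for pregnancy, the loss of at most one radiographic value. All other exit evaluations stay as they are.
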